#### 4.4.2 Adjustment in models

For continuous outcomes that are measured before the treatment has started at baseline as well as subsequently, subsequent values will be modelled, and the baseline value will be modelled as a fixed covariate. Models will be adjusted for stratification factors.

#### 4.4.3 Analysis models

General methods of presentation and assessing treatment effects for all outcomes are outlined below according to data type. As the trial was halted early, only the primary outcome of the trial and the primary outcome of the SWAT will be formerly modelled. The secondary outcomes will be tabulated by treatment group but will not be modelled (i.e. the difference between groups will not be quantified). The secondary outcomes of the SWAT will be tabulated following the 2x2 factorial design groups.

Data type	Outcomes					
Binary	Proportion of participants with any PPC					
Continuous	
 
Load (SWAT outcome)
 
					

Each data type will be summarised and compared between the groups according to the following:

- Binary outcomes will be presented as numbers and percentages of participants in each treatment group. Outcomes will be compared between treatment groups using generalised linear models, with treatment comparison estimates presented as adjusted risk ratios (RR) and risk differences (RD) with 95% CIs.
- Continuous outcomes will be summarised as means and SDs (or medians and IQRs if distributions are skewed). Outcomes will be compared using linear mixed effects methodology with treatment groups and study design variables, and patient terms fitted as random effects. A follow-up x load adjustment method interaction will be fitted; if this is not statistically significant at the 10% level overall treatment effects for follow-up and adjustment method will be reported. If the interaction is statistically significant differences in load between adjustment methods with and without follow-up will be described.

#### 4.4.4 Model assumptions

For all methods outlined underlying assumptions will be checked using standard methods, e.g., residual plots, etc. If assumptions are not valid then alternative methods of analysis will be sought. If outlying observations are found which mean models do not fit the data adequately, such observations will be excluded from the main analyses and comments made in footnotes. Sensitivity analyses may be performed to examine the effect on the study's conclusions of excluding outlying observations.

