## 7. Statistical analyses

### Plan of analysis

The data will be analysed according to ITT and follow CONSORT reporting guidelines. Randomised participants who fail to complete the minimum specified duration of the intervention will be included in the primary analysis.

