Analyses will be adjusted for centre, specialty and ARISCAT score. Differences in treatment effect by specialty/ARISCAT score will be assessed by adding a group x specialty/ARISCAT score interaction to the model and comparing models using a likelihood ratio test. PPCs and other binary outcomes will be compared using logistic regression. Time to event outcomes (e.g. duration of ventilation, ICU and hospital stay) will be analysed using survival methods, allowing for censoring of any participant who dies prior to hospital discharge. HRQoL and MIP will be compared using a mixed regression model, adjusted for baseline measures where appropriate. Changes in treatment effect with time will be assessed by adding a treatment x time interaction to the model and comparing models, again using a likelihood ratio test. Deaths will be accounted for by modelling HRQoL and survival jointly. Model fit will be assessed and alternative models and/or transformations (e.g. to induce normality) will be explored where appropriate. Frequencies of adverse events, including components of the primary outcome, will be described. Treatment effects will be reported with 95% CIs. As the study is not evaluating the surgery per-se, surgical experience is not a criterion for participation (all participants will be under the care of a consultant surgeon). In the context of this study, clustering by surgeon is not relevant to the sample size and can be ignored (on the basis that the intraclass correlation is negligible, personal communication with [name] for a previous study).

A detailed analysis plan will be prepared. Interim analyses will be decided in discussion with the Data Monitoring and Safety Committee (DMSC). There is no intention to compare any outcomes between groups after the completion of Phase 1; the only analyses will be descriptive statistics to summarise eligibility and recruitment to decide whether the study satisfies the recruitment

INSPIRE Protocol Version 2.0 progression criteria and a comparative analysis of the effect of intensive vs. less intensive training in the IMT group on the primary outcome.

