#### 3.3 Analysis populations

#### 3.3.1 Intention-to-treat population

Analyses and summaries will be performed on an intention-to-treat basis. Analyses will use data from all participants randomised. The ITT population will consist of all randomised participants, included according to their randomised allocation, regardless of whether they are ineligible, prematurely discontinue treatment or are otherwise protocol deviators.

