## **SWAT** secondary outcomes

- Change in work (recorded on the IMT device) from baseline;
- Change in MIP from baseline;
- Change in spirometry markers (FEV1 and FVC) from baseline;
- Proportion of participants following at least 80% of the planned training sessions;
- Proportion of participants training at the prescribed intensity score of (RPE rating) ≥5

New variable	Rules
Change in load	

load on last line of patients diary – load at initial training visit

Change in work	

work in joules on last line of patients diary – work in joules at initial training visit

Change in MIP	= MIP on day of surgery – MIP at baseline
Change in spirometry markers (FEV 1 and	= FEV 1 on day of surgery – FEV 1 at baseline
FVC) from baseline	= FVC on day of surgery – FVC at baseline
Proportion of participants following at least 80% of the planned training sessions – recorded on patient diary	YES: If more than 22 (80% of planned 28) energy measurements are recorded on the patient diary
	NO: If 22 or less (80% of planned 28) energy measurements are recorded on the patient diary
	MISSING: otherwise
Proportion of participants following at least 80% of the planned training sessions – recorded on KHP2 device	YES: If more than 22 (80% of planned 28) energy measurements are recorded on the KHP2 device
	NO: If 22 or less (80% of planned 28) energy measurements are recorded on the KHP2 device
	MISSING: otherwise
Proportion of participants training at the prescribed intensity score of RPE rating ≥5	YES: If participant reported an RPE of 5 and above on their first, second and last line of patients diary
	NO: If participant reported at least one RPE below 5 on their first, second or last line of patients diary
	MISSING: otherwise
Proportion of participants training at the prescribed intensity score of RPE rating ≥5 – additional visit measurements	YES: If participant reported all RPE values of and above during the most recent 10 training sessions at their additional visit

(participants randomised to additional visit only)

**NO:** If participant reported at least one RPE below 5 during the most recent 10 training sessions at their additional visit

MISSING: otherwise

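### SAP 4.4.4 deletes outlying values from the main analyses on an undefined model-fit judgement, against the SAP's own ITT rule; for SWAT training load this can bias the estimate either way and narrows its confidence interval

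*SAP*

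**What the plan says.** SAP 4.4.4 (Model assumptions) first sends failed assumptions to other methods of analysis. It then adds a separate rule for outlying observations that stop a model fitting adequately: "such observations will be excluded from the main analyses and comments made in footnotes". The only safeguard is permissive: "Sensitivity analyses may be performed to examine the effect on the study's conclusions of excluding outlying observations".

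SAP 3.3.1 (Intention-to-treat population) says: "Analyses will use data from all participants randomised". Protocol 7 (Plan of analysis) agrees: "The data will be analysed according to ITT and follow CONSORT reporting guidelines". For poor fit, Protocol 7.1.2 offers something other than deletion: "Model fit will be assessed and alternative models and/or transformations (e.g. to induce normality) will be explored where appropriate".

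The rule reaches only two models, because after early closure "only the primary outcome of the trial and the primary outcome of the SWAT will be formerly modelled" (SAP 4.4.3). One is any PPC, which is binary. The other is SWAT training load, whose change is defined in SAP 4.3 as "load on last line of patients diary – load at initial training visit".

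**The concern.** Exclusion is compulsory, applies to the main analysis, and is decided after looking at the fitted model. The SAP does not say what counts as outlying, does not require evidence of a recording error, and does not require the decision to be made blind to allocation. The full-data result need never be shown; a footnote satisfies the text.

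Whether load is analysed as a change or as the final value adjusted for baseline (SAP 4.4.2), each participant has one post-baseline value. Removing it therefore removes a randomised participant because of their outcome. Two things are at stake: whether the randomised comparison is preserved, and whether the reported interval reflects the real spread of the data.

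**Working it through.** **1. Reproduce the plan's SWAT precision.** Inputs from SAP 2.4.2: 160 participants, 40 per cell, so 80 v 80 for a main effect. Half-width in SD units = critical value × √(2/n).
- n = 80: 1.96 × √(2/80) = 0.310 (0.312 with the t distribution). Stated: 0.31.
- n = 40: 1.96 × √(2/40) = 0.438 (0.445 with t). Stated: 0.45.

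The plan's figures reproduce. They assume that all values are kept.

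**2. Effect of exclusion on the interval.** Simulation, 20,000 trials per setting, 80 v 80, unit SD, two-group t model. Values are dropped when the residual exceeds k SD. The SAP gives no cut-off, so k = 2, 2.5 and 3 are assumptions. With normal errors:

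| k | half-width (all data 0.312) | coverage of 95% CI |
|---|---|---|
| 2 | 0.281 | 89% |
| 2.5 | 0.300 | 93% |
| 3 | 0.308 | 94.5% |

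With heavier-tailed or skewed errors of the same shape in both arms (t5, t3, exponential, log-normal), coverage was 91% to 94%. With all data kept it stayed at about 95%. The interval narrowed in every continuous setting.

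**3. Effect on the estimate.** The true difference was set at 0.53 SD. The protocol's sample size section gives that figure for MIP; using it for load is an assumption.
- Residual-based exclusion, same error shape in both arms: 0.529 to 0.532, so no shift.
- Exclusion on pooled values, ignoring group: 0.425 to 0.520, so it shrinks.
- Long tail of high responders in the better arm: 0.374, 0.425 and 0.458 at k = 2, 2.5 and 3; coverage 72%, 84% and 90%.
- Long tail of poor responders in that arm: 0.687, 0.636 and 0.599; coverage 72%, 84% and 90%. Here it grows.

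**4. Skewed data with a multiplicative effect.** Log-normal load, untransformed, 80 v 80, k = 3, 5,000 trials per setting. True difference = (ratio − 1) × exp(log-SD²/2). The log-SDs and ratios are assumptions.

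| log-SD, ratio | true | after exclusion | shrinkage | coverage |
|---|---|---|---|---|
| 0.5, 1.3 | 0.340 | 0.304 | 1 − 0.304/0.340 = 11% | 91% |
| 0.7, 1.6 | 0.767 | 0.635 | 1 − 0.635/0.767 = 17% | 83% |
| 0.9, 1.6 | 0.900 | 0.688 | 1 − 0.688/0.900 = 24% | 81% |

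About 2.5 to 3.3 participants are removed per trial. If the same data are analysed on the log scale, about 0.4 are removed, the estimates are unbiased, coverage is 94% and the interval is 1% narrower.

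**5. Binary PPC.** A 0/1 outcome has no extreme values, but an event at fitted risk p has Pearson residual √((1 − p)/p): 2.38 at 15%, 2.00 at 20% and 3.0 at 10%. Assume two equal strata with control risks 12% and 28% and a risk ratio of 0.75, so IMT risks are 9% and 21%. The residuals for an event are 2.71 and 1.60 (control), and 3.18 and 1.94 (IMT).
- Cut-off 3 deletes events only in the low-risk IMT stratum. IMT risk becomes 0.105/0.955 = 11.0%, against 20% for control. The risk difference goes from −5.0 to −9.0 points (risk ratio 0.55).
- Cut-offs 2 and 2.5 also delete the low-risk control events. Control risk becomes 0.14/0.94 = 14.9%, and the risk difference is −3.9 points (risk ratio 0.74).

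This shows what a literal reading would permit, not what the SAP intends.

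**The case against.** The best defence is the sentence in SAP 4.4.4 just before the exclusion rule, which calls for other methods when assumptions fail; the protocol names transformations. Followed first, that route removes nearly all the harm from skewness, as the log-scale result in step 4 shows. This stands as to size. It does not rescue the rule: 4.4.4 does not say that exclusion comes only after a transformation has failed, and it still makes exclusion compulsory.

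A reader might infer that the rule pulls the SWAT effects towards no difference because the best responders would be deleted. The documents do not support that. They give no distribution for load. The 5% increments apply only to the manual arms; in the automatic arms the device sets load from estimated MIP. The manual look-up table moves by one whole unit for every load from 10 to 29, and an increase requires a perceived exertion rating of 5 or less. Step 3 shows no shift, shrinkage or growth, depending on the tail and the flagging method.

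Load is also read from a patient diary, so some outlying values may be recording errors. That is a fair reason to verify and correct them, and SAP 4.6 already provides for data cleaning. It is no reason to delete values not shown to be wrong.

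Finally, the SAP is marked v0.3, and its section 7 expects sign-off of v1.0 before any analysis, so the text can still be corrected.

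**Conclusion.** The rule is wrong as written, with moderate severity. It conflicts with SAP 3.3.1 and with the protocol's remedy for poor fit, whichever way it would move the result. For SWAT load, deleting genuine values makes the interval too narrow and can bias the estimate in either direction. The size depends on the unstated cut-off and distribution: almost nothing with normal errors at 3 SD, but coverage of 81% to 91% for untransformed log-normal data with a multiplicative effect, and lower still (72% at 2 SD) when only one arm has a long tail. All these figures use the planned 80 v 80. SAP 1.1.2 reports a reduced sample size, and the achieved SWAT number is not given.

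Two stronger readings should be resisted. A biased SWAT result would not misdirect the choice of delivery mode for Phase 2, because the funder closed the study and recruitment ended with Phase 1. Nor do the documents show that the trial's primary PPC comparison is compromised; there the defect is a rule with no clear meaning that could be read as licence to delete events.

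**What to change.** Replace the exclusion sentences in SAP 4.4.4 with text to this effect:
- All verified observations are kept in the main analysis.
- A value is corrected or removed only if confirmed as a data error, with the decision made blind to allocation and documented.
- Poor fit is handled by transformation (for example, log load) or by robust or bootstrap methods.
- Any analysis that excludes outliers is a sensitivity analysis only, with a cut-off set in advance, reported beside the full-data result.
- The exclusion rule does not apply to the binary PPC outcome.

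The cost is SAP wording only. No data collection or design change is needed, and it can be done at v1.0 sign-off.

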#### 4.5 General content

## 4.5.1 Participant flow

The CONSORT flow diagram will be used to summarise the flow of participants through screening until follow-up throughout the course of the study (see Figure A1).

Protocol deviations defined in section 0 will be summarised by treatment group. The number of withdrawals of consent will be presented, along with reasons for withdrawal.

#### 4.5.2 Baseline data

Baseline data (i.e. patient demography) will be described by treatment group and separately by surgical specialty for participants in the ITT analysis population. The thoracic and abdominal surgical specialties will be combined into one non-cardiac speciality as there were too few participants recruited in the thoracic specialty when the trial was halted.

Continuous variables will be summarised using the mean and standard deviation (SD) (or median and inter quartile range (IQR) if the distribution is skewed), and categorical data will be summarised as a number (n/N) and percentage.

Any imbalances in the characteristics of the participants at the start of the study will be described but statistical tests for baseline imbalance will not be carried out.

#### 4.5.3 Intervention

The intervention adherence will be described by surgical specialty (cardiac and non-cardiac surgery)

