#### 2.1.1 Internal pilot (Phase 1)

INSPIRE will have an internal pilot (Phase 1) to:

- i. describe recruitment rates:
- ii. describe participants' adherence to the IMT protocol (i.e. following the instructions to carry out IMT twice per day at the correct intensity);
- iii. determine whether an additional 'virtual' follow up meeting conducted via telephone or video call (within one week of starting the intervention, ideally day 3 to 5) improves adherence to the IMT protocol and the effectiveness of the training as determined by the progression in training load:
- iv. determine whether adjusting the training load automatically using the IMT device improves adherence to the IMT protocol and the effectiveness of the training as determined by the progression in training load;
- v. determine whether there is any contamination between intervention and control groups.

Phase 1 will define the optimal mode of delivery of the IMT intervention, which will be used in the main trial (Phase 2). Phase 1 will take place in a minimum of four UK hospitals.

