#### 2.1.3 Main study (Phase 2)

Progression criteria from Phase 1 to Phase 2:

- all centres participating in the pilot are recruiting (in one or more specialties);
- at least 40% of eligible patients are consenting to randomisation;
- each centre recruiting >8 patients/month (from any specialty);
- interventions are delivered according to the protocol in all centres;
- the allocated intervention is initiated in >=90% of randomised participants;
- >=70% of patients randomised to high resistance IMT or low IMT adhere to allocated interventions (adherence will be recorded electronically by the IMT device); we will define a patient as adherent with the intervention if they use the IMT device at least five days a week (for a minimum of 30 breaths per day).

If progression criteria are met, recruitment will continue at the Phase 1 hospitals and we will begin recruitment at a minimum of an additional two hospitals (depending on how recruitment is going in Phase 1). Delivery mode of the intervention will be based on the findings in Phase 1 and any amendments to the study will be submitted for approval by the regulatory authorities.

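### The SAP's IMT adherence variable is planned by surgical specialty but not by randomised arm, and the SWAT adherence outcomes are shown in four cells with no estimate for either delivery factor

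*SAP*

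**What the plan says.** SAP 4.5.3 is one sentence: "The intervention adherence will be described by surgical specialty (cardiac and non-cardiac surgery". The variable of that name is defined within SAP 4.3.2, under the heading on adherence to training. It is a yes/no rule that combines days per week with a session, weeks of training and breaths per day.

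The table shells treat adherence as follows.

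- **Table A11** has columns for the randomised groups but no adherence row.
- **Table A8** lists protocol deviations by specialty and is repeated by allocation. Its rows include non-adherence, too short a training period, no training at all and, for the high resistance arm, insufficient intensity. SAP 3.3.2 and 4.5.1 also present deviations by allocation.
- **Table A10** covers only the high resistance arm, in four SWAT cells. It includes the proportion completing at least 80% of planned sessions, by diary and by device.

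SAP 2.1.1 makes adherence a pilot objective, explained as "following the instructions to carry out IMT twice per day at the correct intensity". Objective iv is to "determine whether adjusting the training load automatically using the IMT device improves adherence to the IMT protocol". Objective iii is to "determine whether an additional 'virtual' follow up meeting conducted via telephone or video call" has the same benefit, and both end with the wording "improves adherence to the IMT protocol and the effectiveness of the training as determined by the progression in training load". The progression criterion in SAP 2.1.3 is ">=70% of patients randomised to high resistance IMT or low IMT adhere to allocated interventions".

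SAP 4.4.3 limits modelling to the two primary outcomes because the trial was halted early, and adds: "The secondary outcomes of the SWAT will be tabulated following the 2x2 factorial design groups".

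**The concern.** The trial closed at the pilot stage, so adherence to high resistance training, and what improves it, are among the main things it can still report. Two gaps stand in the way.

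First, a table by specialty mixes two unlike regimens. The high resistance arm starts at 50% of MIP and progresses (Protocol 5.6.3.2). The low resistance arm breathes gently at a fixed 10% of MIP (Protocol 5.6.4). A pooled figure describes neither arm. Neighbouring sections do name the arm: SAP 4.5.1 for deviations, 4.5.2 for baseline data and 4.5.5 for subgroups. SAP 4.5.3 gives no reason for leaving it out.

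Second, objectives iii and iv are comparative, and each concerns one factor of a 2x2 design. Four unsummed cells show neither factor's effect directly and leave unused the precision that the factorial layout provides.

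**Working it through.** **1. The plan's own precision figures.** SAP 2.4.2 plans 160 high resistance participants, 40 per cell, hence 80 per factor level. The half-width in SD units is quantile x sqrt(2/n).

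- Main effect, n = 80 per level: 0.310 (normal) or 0.312 (t). Stated: 0.31.
- Within one meeting stratum, n = 40 per cell: 0.438 (normal) or 0.445 (t). Stated: 0.45.

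Both reproduce, the second with the t quantile. They apply to training load, the only SWAT outcome still modelled.

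**2. The same contrast for adherence.** The half-width for a difference in proportions is 1.96 x sqrt(2p(1-p)/n). Take p = 50%, the widest case.

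- Factor margin, 80 v 80: 1.96 x sqrt(0.5/80) = 0.155, or 15.5 points.
- One cell pair, 40 v 40: 1.96 x sqrt(0.5/40) = 0.219, or 21.9 points.

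The earlier pragmatic trial described in Protocol 2.4 had 54% completing at least 80% of sessions. At that rate the figures are 15.4 and 21.8 points. At 70% they are 14.2 and 20.1.

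**3. Smaller recruitment.** SAP 1.1.2 refers to a reduced sample size without giving it. The totals below are assumptions, at p = 50%.

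- 80 high resistance participants, margin 40 v 40: 1.96 x sqrt(0.5/40) = 0.219, about 22 points.
- 40 high resistance participants, margin 20 v 20: 1.96 x sqrt(0.5/20) = 0.310, about 31 points.

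**4. What pooling can hide.** Randomisation is 2:1:1 (SAP 2.2), so the device arms are about 2:1. Pooled adherence is (2 x high + low)/3, which gives high = (3 x pooled - low)/2. With pooled = 0.70:

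| Low resistance (assumed) | High resistance |
|---|---|
| 90% | (2.10 - 0.90)/2 = 60% |
| 95% | (2.10 - 0.95)/2 = 57.5% |
| 100% | (2.10 - 1.00)/2 = 55% |
| 60% | (2.10 - 0.60)/2 = 75% |

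The last row shows that pooling can mislead in either direction.

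**5. Whether Table A10 can stand in for the adherence variable.** SAP 4.3.2 counts SWAT session adherence as more than 22 of 28 sessions. The adherence variable needs a session on at least five days a week for at least two weeks, with at least 30 breaths a day. A participant who does one 30-breath session daily for exactly 14 days has 14 sessions. That person is adherent on the second rule and, since 14 is not above 22, non-adherent on the first. Table A10 also contains no low resistance participants.

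**The case against.** The best reply is that most of this can already be found or derived.

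- **Arm-level reporting may be implied.** SAP 4.4.1 and 4.4.3 say secondary outcomes are shown by group, and the adherence variable is defined inside the secondary outcome section. This has some force. But the variable is not in the protocol's list of secondary outcomes (Protocol 5.7.2), Table A11 has no row for it, and the one sentence on how to present it names only specialty.
- **Non-adherence does appear by arm.** Table A8 shows it by allocation. This stands, so a reader should not infer that the SAP gives adherence information by specialty only. However, Table A8 counts deviations, including excess training, and no row states the adherence rule.
- **Low resistance adherence cannot enter Table A10.** Its cells make up the high resistance arm, and both margins can be recovered by adding them. This also stands. A reader might infer that the pilot's adherence questions go unanswered, or that a null PPC result could not be interpreted. Neither follows.
- **The delivery decision rested on training load**, which is modelled with both factors and their interaction (SAP 2.1.2, 4.4.3). The closing words of objectives iii and iv can be read as making load the measure of both adherence and effectiveness. Even so, the SWAT has separate session-adherence outcomes, and they get no contrast.
- **Leaving secondary outcomes unmodelled is a declared choice** after early closure. It is not an oversight, and a contrast on adherence would be an exception to it.
- **The 70% criterion no longer governs a decision.** A reader might want it judged on the high resistance arm alone. The protocol and SAP both word it over the two device arms, and changing it after closure would be post hoc.

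**Conclusion.** The point holds as a gap in presentation and estimation. The derived adherence variable has no stated by-arm output, and the two comparative adherence objectives get no direct estimate. No alpha level, power, sample size or primary analysis is affected.

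The masking figures of 60%, 57.5% and 55% rest on assumed low resistance adherence of 90%, 95% and 100%. The documents give no adherence data for that regimen. They support the statement that pooling could conceal a gap between arms, not that it will or in which direction.

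The gain from using margins is a half-width smaller by a factor of sqrt(2): 15.5 against 21.9 points at the planned 160 and 50% adherence. With fewer participants the margins may be too wide to settle either question. An interval would make that visible, whereas four bare percentages would not.

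**What to change.** 1. In SAP 4.5.3, and as a row in Table A11, report the derived adherence variable by randomised device arm, and by specialty within arm, with 95% CIs.
2. Report the pooled 70% criterion as worded, with each device arm's figure beside it. Do not redefine it.
3. In SAP 4.4.3 and Table A10, keep the four cells and add a high resistance total and the two factor margins. For the session-adherence outcomes, add a descriptive main-effect risk difference for each factor, with a 95% CI and no p-value. State this as an exception to the rule that differences in secondary outcomes are not quantified.
4. Before tabulating, reconcile the definition in SAP 4.3.2. The rule for non-adherence repeats the breath condition of the rule for adherence, so the variable is ambiguous as written.

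The cost is a few sentences and some extra rows and columns, with no new data. The downside is one more contrast per delivery factor for session adherence, secondary and probably imprecise, and a small departure from the no-quantification rule.
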